6.5 Partial Dates

6.5.1 Adverse Events

End date will be imputed first. Start date imputed based on imputed end date. If year of the date is missing, the date will be imputed according to the following rules.

End date:

- 1) If ongoing is checked, no imputation will be performed.
- 2) If ongoing is not checked and end date is totally missing, then end date will be imputed as date of the last visit.
- 3) If only day of end date is missing, end date will be imputed as the earlier one of following dates: the last day of that month and date of the last visit.
- 4) If only month (or both month and day) of end date is missing, end date will be imputed as the earlier one of following dates: the last day (Dec31) in that year and date of the last visit.

Start date:

- 1) If start date is totally missing and end date is also missing (ongoing), no imputation will be performed.
- 2) If start date is totally missing and end date is not missing, start date will be imputed as the earlier one of following dates: end date of AE and date of the first dose of study medication.

- 3) If only day of start date is missing, and start date is in the same month of first study medication, start date will be imputed as earlier one of following non-missing dates: end date of AE and date of the first dose of study medication.
- 4) If only day of start date is missing, and start date is not in the same month of first study medication, start date will be imputed as the first day in that month.
- 5) If only month (or both month and day) of start date is missing, and start date is in the same year of first study medication, start date will be imputed as earlier one of following non-missing dates: end date of AE and date of first dose of study medication.
- 6) If only month (or both month and day) of start date is missing, and start date is not in the same year of first study medication, start date will be imputed as the first day (Jan01) in that year.

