### **10.1 Study Medication**

The study drug (patches) will be applied to the subject's back, chest, or abdomen once daily around the same time of the day from the beginning of the washout phase until the end of the open-label treatment phase. All patches for each day should be applied to only one location, ie, the back, the chest, or the abdomen. The study drug will be replaced every day. When the study drug patches are to be replaced, the new patches will be applied to the location different from that of the last application, or a site different from that of the last application on the same location.

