#### 10.1.1 The Washout Phase

After obtaining informed consent, 2 placebo patches will be applied once daily to the eligible subjects (Section 8.1 Criteria at screening, p29) for 1 week in principle, but at least 3 days, in a single-blind manner.

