## **12. SAFETY REPORTING**

### **12.1 Definitions**

#### **12.1.1 Adverse Events**

An adverse event (AE) is any untoward medical occurrence in a study subject administered a medicinal (investigational) product and which does not necessarily have a causal relationship with this treatment. An AE can, therefore, be any unfavorable and unintended sign (including an abnormal laboratory finding), symptom, or disease occurring after the administration of a medicinal (investigational) product, whether or not considered related to the medicinal (investigational) product. AEs may include the onset of new illness and the exacerbation of pre-existing conditions. AEs will be collected from the beginning of the study treatment in the washout phase until the follow-up visit. AEs also include other untoward events occurring from the beginning of the study treatment in the washout phase until the follow-up visit, for instance, events occurring in association with study-related procedures or assessments, or those occurring under placebo treatment.

AEs that occur during the washout phase and worsen during the double-blind treatment phase will be recorded as AEs in the washout phase and also as AEs in the double-blind treatment phase. AEs that occur during the washout phase and worsen during the open-label treatment phase will be recorded as AEs in the washout phase and also as AEs in the open-label treatment phase. The date of worsening will be

recorded as the onset date of the worsening AE. Likewise, AEs that occur during the double-blind treatment phase and worsen during the open-label treatment phase will be recorded as AEs in the double-blind treatment phase and also as AEs in the open-label treatment phase, with the date of worsening as the onset date. In addition, AEs that occur during the washout phase or double-blind treatment phase without further worsening in the following phase will be recorded as AEs in the washout phase or as AEs in the double-blind treatment phase, respectively.

Lack of efficacy may be an expected potential outcome and should not be reported as an AE unless the event is unusual in some way. New signs and symptoms of the underlying disease, or signs and symptoms of an emerging disease should be recorded as AEs.

The Investigator should attempt to establish a diagnosis of the event based on signs, symptoms, and/or other clinical information. In such cases, the diagnosis should be recorded as the AE and not the individual signs/symptoms.

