7.4.3 Prior and Concomitant Medications

Medications received prior to or concomitantly with treatment will be coded by Covance using the WHO Drug Dictionary [March 1, 2014 version], Anatomical Therapeutic Chemical (ATC) Classification codes.

Prior medications and concomitant medications are defined as follows:

Statistical Analysis Plan

Version: 2

Study No. D4904020

Prior medications are defined as those taken prior to initial dose of study medication, ie, those medications with a start date before the date of initial application of study medication in the double-blind treatment phase.

Concomitant medications are defined as those taken during the double-blind treatment phase and the DSP-5423P treatment period as described below. Note that the concomitant and prior medications definitions are not mutually exclusive, ie, a medication can be classified as both prior and concomitant.

For the double-blind treatment phase, concomitant medications are those with a start date on or after the initial application date of double-blind treatment phase and up to the final application date of double-blind treatment phase, or those with both a start date before the initial application date of double-blind treatment phase and an end date on or after the initial application date of double-blind treatment phase.

For the DSP-5423P treatment period, concomitant medications are those with a start date on or after the first date of DSP-5423P treatment but before the final application date of DSP-5423P treatment, and those with both a start date before the initial application date of DSP-5423P treatment and an end date on or after the initial application date of DSP-5423P treatment.

If a start date of medication is missing after applying imputation rules, the corresponding medication will be classified as concomitant medication. Note that this is only applicable if the initial application date of study medication is not missing.

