7.7.1 Adverse Events

Treatment emergent AEs (TEAEs) are defined as follows:

- TEAEs (the double-blind treatment phase): Events with start date on or after the date of initial application of study drug in the double-blind treatment phase, and up to 17 days after the date of final application of study drug in the double-blind treatment phase and before the first application of DSP-5423P in the open-label treatment phase.
- TEAEs (DSP-5423P treatment period): Events with start date on or after the date of initial application of DSP-5423P either in the double-blind treatment period for 40MG and 80MG groups or in the open-label treatment period for placebo group and up to 17 days after the date of final application date of DSP-5423P.

AE with missing or incomplete start date after imputation will be considered as TEAE.

Treatment-related TEAE:

A treatment-related TEAE is defined as a TEAE for which the causal relationship to the study treatment is either 'definite', 'probable', or 'possible'.

Common TEAE:

Common TEAE in the double-blind treatment phase are PT of TEAEs experienced by 2% or more subjects in 40MG or 80MG group in the safety population.

Common TEAE in the DSP-5423P treatment period are PT of TEAEs experienced by 2% or more subjects in the overall-to-FLEX DOSE group in the DSP-5423P dosed population.

The summary of AEs will be limited to treatment-emergent AEs (TEAEs). The number and percentage of subjects with TEAEs during the double-blind treatment phase on the safety population and DSP-5423P treatment period on the DSP-5423P dosed population will be summarized by preferred term, system organ class, and treatment group. Summaries will be repeated by country and race.

Specifically, this will cover the following items:

- any TEAE;
- TEAE leading to death;
- TEAE leading to treatment discontinuation;
- serious TEAE;

- extrapyramidal TEAE;
- skin-related TEAE;
- treatment-related TEAE;
- treatment-related TEAE leading to death;
- treatment-related TEAE leading to treatment discontinuation;
- treatment-related serious TEAE;
- treatment-related extrapyramidal TEAE;
- treatment-related skin-related TEAE;

Skin-related TEAE is defined as the TEAE occurred at the application site (recoded in the CRF) and identified as TEAE with a wording “Application site” in MedDRA LLT.

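### Imputed AE start dates have no floor at the first DSP-5423P application, so some placebo-first subjects' open-label events can drop out of the DSP-5423P TEAE tables

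*SAP*

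**What the plan says.** SAP section 6.5.1 has six start-date rules.

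- Rule 1: start wholly missing and event ongoing. Nothing is imputed.
- Rule 2: start wholly missing, end known. The start is the earlier of the end date and the first dose.
- Rule 3: only the day missing, in the month of first dosing. The start is "imputed as earlier one of following non-missing dates: end date of AE and date of the first dose of study medication".
- Rule 4: only the day missing, any other month: "start date is not in the same month of first study medication, start date will be imputed as the first day in that month".
- Rule 5: month missing, same year as first dosing. As rule 3.
- Rule 6: month missing, any other year: "start date will be imputed as the first day (Jan01) in that year".

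SAP section 7.7.1 defines double-blind TEAEs as "Events with start date on or after the date of initial application of study drug in the double-blind treatment phase", closing 17 days after the last double-blind application and before any open-label DSP-5423P. The DSP-5423P treatment-period window opens at the first DSP-5423P application, which for the placebo arm is in the open-label phase. A fallback counts an event as treatment-emergent only if its start is still missing or incomplete after imputation.

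Section 6.5.1 does not say which first dose it means. Under Protocol section 10.1, study drug is applied daily "from the beginning of the washout phase until the end of the open-label treatment phase". Section 10.1.1 adds that in washout "2 placebo patches will be applied once daily to the eligible subjects". Section 12.1.1 states: "AEs will be collected from the beginning of the study treatment in the washout phase until the follow-up visit". SAP section 7.4.3, however, explains its own initial-dose wording, for prior medications, as "those medications with a start date before the date of initial application of study medication in the double-blind treatment phase".

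**The concern.** SAP section 6.2 defines On-treatment Day 1, but no imputation rule refers to it. For a subject randomised to placebo, that date divides placebo from drug exposure, and an imputed start that ignores it can put an on-drug event on the wrong side. The fallback in section 7.7.1 does not recover the event, because an imputed date is complete. The result is perverse: an ongoing event with no start date is counted as treatment-emergent, while one with a known month may be excluded.

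Long-term safety is a secondary objective. For events with only the day missing, the loss falls on the first weeks of drug exposure in placebo-first subjects. The undefined first-dose term raises a second question: whether double-blind events could be dated into washout.

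**Working it through.** The plan states no figure on this point, so the check applies the rules to dates.

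**Worked example (illustrative dates).** Washout starts 3 March, Day 1 is 10 March, and the first open-label patch is 21 April (Day 1 + 42 days; Protocol section 7.1 gives 6 weeks of double-blind treatment).

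- Placebo-first subject, true onset 28 April, day missing. April is not the first-dose month on either reading, so rule 4 gives 1 April. That is before 21 April and outside the DSP-5423P window.
- Any arm, true onset 20 March, day missing. Rule 3 gives 3 March if the first dose is the washout patch (before Day 1, not a TEAE), or 10 March if it is Day 1 (a TEAE).

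The switch comes about 42 days after Day 1, which is longer than any month. The switch month is therefore never the first-dose month, and rule 4 always governs it.

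**Hand calculation for rule 4.** In a 30-day month with the switch on day d (d = 2 to 30), onsets on days d to 30 are misdated, which is 31 − d days. The sum is 29 + 28 + … + 1 = 435, and 435/30 = 14.5 days on average. Over 196 open-label days (28 weeks) this is 14.5/196 = 7.4%. Over 364 days (52 weeks, Japan) it is 14.5/364 = 4.0%.

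**Enumeration over 365 Day 1 dates.** Assumptions not in the documents: onset uniform within phase, event lasting 7 days, 42-day double-blind phase, 196-day open-label phase starting the next day. Washouts of 3 and 7 days gave the same results.

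| True onset | Missing | First dose = washout patch | First dose = Day 1 |
|---|---|---|---|
| Open-label, dated before first open-label patch | day | 7.5% | 7.5% |
| As above, onset in first 28 open-label days | day | 52.4% | 52.4% |
| Open-label, dated before first open-label patch | month | 73.0% | 73.0% |
| Open-label, dated before first open-label patch | all, end known | 100% | 100% |
| Double-blind, dated before Day 1 | day | 35.0% | 0% |
| Double-blind, dated before Day 1 | month | 94.1% | 0% |
| Double-blind, dated before Day 1 | all, end known | 100% | 0% |

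The 7.5% agrees with the hand calculation. The 73.0% combines rule 5 (onset in the calendar year of first dosing) with rule 6 (1 January falling before a switch in the new year). On the washout reading it splits into 61.5% dated before Day 1 and 11.5% dated in the double-blind phase.

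The open-label rows mean loss from the DSP-5423P tables only for placebo-first subjects. In the 40 and 80 mg arms the window opens at Day 1, so an event moved back into the double-blind phase stays inside it, and only its phase, first-onset interval or dose at onset can be wrong.

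**The case against.** The case for leaving the rule alone has real content.

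- SAP section 7.4.3 ties very similar words to the first double-blind application. On that reading no double-blind event is lost. This stands as far as it goes, but the passage serves prior medications only and the protocol's usage points to washout. The term is ambiguous, and a reader who takes washout dating as settled goes beyond the documents.
- A reader might infer that back-dated events are added to the placebo column of the double-blind tables. That is not shown. SAP section 7.9 runs the double-blind analysis on its own database and combines the two later. The imputed date falls in the placebo phase, but the event may simply be absent from the DSP-5423P tables.
- A reader might also infer that every day-missing event in the switch month is misplaced. It is not. That month usually contains placebo days too, and an event that truly began on placebo is assigned correctly.
- Nor does the rule favour drug in the randomised comparison. Any washout dating would affect all arms.
- Partial dates should be uncommon. Subjects are in hospital to Day 14, open-label visits fall at Weeks 1, 2 and 4, and the start date is a minimum item of the first SAE report. Section 7.7.1 plans no statistical comparison of AEs, and safety data are also listed, so no event is hidden.

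These points limit the consequence. They do not remove the missing floor, which acts on either reading.

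**Conclusion.** The point holds in a narrow form. A stated rule, followed exactly, can take a placebo-first subject's on-drug event out of the DSP-5423P treatment-period TEAE tables. This happens for day-missing onsets after the switch in the switch month (unless open-label Day 1 is the 1st), for wholly missing starts with a known end, and for many month-missing starts.

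The percentages rest on uniform onset and apply only to partial dates. Their number is not given, so the effect on any table cannot be stated and is probably small. Loss of double-blind events is conditional on the washout reading. This is a minor defect, worth correcting because the correction is cheap.

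**What to change.** In SAP section 6.5.1:

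1. Replace the first-dose term with the initial application in the double-blind treatment phase (Day 1).
2. For AEs recorded in the open-label phase, floor the imputed start at the first open-label application. For AEs recorded in the double-blind phase, floor it at Day 1. Apply the floor whenever the known month and year are compatible with it and the AE end date is not earlier.
3. State that an AE recorded in washout is dated no later than the day before Day 1. Otherwise the new anchor could pull it forward to Day 1.
4. Correct the lead-in to the rules, which speaks of a missing year although rules 3 to 6 need a known one.

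Protocol section 12.1.1 already has AEs recorded by phase. Using that phase gives each AE a single imputed start date, so no event is counted in two tables under two dates. If the recorded phase is right, no on-treatment event leaves its window. Step 1 alone would protect double-blind events but leave the 7.5% of day-missing open-label events misdated.

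The cost is SAP wording and matching programming. The downside is that an event recorded in one phase but truly begun slightly earlier may count as treatment-emergent in that phase.

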6.5.2 Prior/Concomitant Medication

If year of the date is missing, the date will be imputed according to the following rules.

End date:

- 1) If ongoing is checked, no imputation will be performed.
- 2) If ongoing is not checked and end date is totally missing, then end date will be imputed as date of the last visit.
- 3) If only day of end date is missing, end date will be imputed as the earlier one of following dates: the last day of that month and date of the last visit.
- 4) If only month (or both month and day) of end date is missing, end date will be imputed as the earlier one of following dates: the last day (Dec31) in that year and date of the last visit.

Start date:

- 1) If start date is totally missing, no imputation will be performed. If the medication is 'started prior to study' (checked in the CRF), then the medication is set to be a prior medication. Otherwise, the medication is neither prior nor concomitant.
- 2) If only day of start date is missing, start date will be imputed as the first day in that month.
- 3) If only month (or both month and day) of start date is missing, start date will be imputed as the first day (Jan01) in that year.

6.5.3 First/Current Episode of Schizophrenia

For the purpose of the estimation of disease duration, the day of onset date of first/current episode will be imputed as the first day in that month.

- 1) If onset date is totally missing, no imputation will be performed.
- 2) If only month of onset date is missing, and onset date is not in the same year of informed consent, onset date will be imputed as June 30th.
- 3) If only month of onset date is missing, and onset date is in the same year of informed consent, onset date will be imputed as previous day of informed consent.

6.6 Pooled Center

Some centers may have less than 10 subjects, and these will be pooled. The pooling system works as follows: For each country, rank the centers by ascending order by site ID, combine the centers to ensure there are at least 20-30 subjects in each pooled center. Pooled centers will be determined before unblinding, and the list of pooled centers will be attached in the SAP (Appendix II).

6.7 Antipsychotics, antiparkinson drugs, psychotropic drugs, and hypnotic drugs

Classification of prior and concomitant drugs will be based on the category chosen in Prior and Concomitant Medications CRF forms.

6.8 Rating Scales

6.8.1 Positive and Negative Syndrome Scale (PANSS)

The PANSS is an interview-based measure of the severity of psychopathology in adults with psychotic disorders. The patient is rated from 1 to 7 on 30 different items across three subscales. A score of 1 indicates absence of symptoms absent while 7 indicates extreme symptoms.

The PANSS total score will be calculated as the score sum of all 30 items, and it ranges from 30 (least severe) to 210 (most severe).

The PANSS positive subscale is defined as the score sum of all 7 items within this subscale. The possible values are 7 (least severe) to 49 (most severe). The 7 items are delusions, conceptual disorganization, hallucinatory behavior, excitement, grandiosity, suspiciousness/persecution, and hostility

The PANSS negative subscale is defined as the score sum of all 7 items within this subscale. The possible values are 7 (least severe) to 49 (most severe). The 7 items are blunted affect, emotional withdrawal, poor rapport, passive/apathetic social withdrawal, difficulty in abstract thinking, lack of spontaneity and flow of conversation, and stereotyped thinking

The PANSS general psychopathology subscale is defined as the score sum of 16 items within this subscale. The possible values range from 16 (least severe) to 112 (most severe). The 16 items are somatic concern, anxiety, guilt feelings, tension, mannerisms and posturing, depression, motor retardation, uncooperativeness, unusual thought content, disorientation, poor attention, lack of judgment and insight, disturbance of volition, poor impulse control, preoccupation, and active social avoidance

Additionally, the PANSS five-factor model will also be considered, which is based on the sum of the following items:

Negative symptoms: Blunted affect, emotional withdrawal, poor rapport, passive/apathetic social withdrawal, lack of spontaneity and flow of conversation, and active social avoidance

Excitement: Excitement, hostility, tension, and poor impulse control

Cognitive disorders: Conceptual disorganization, difficulty in abstract thinking, mannerisms and posturing, disorientation, and poor attention

Positive symptoms: Delusions, grandiosity, suspiciousness/feelings of persecution, and unusual thought content

Anxiety/depression: Hypochondria, anxiety, feelings of guilt, depression, and Preoccupation

6.8.2 Clinical Global Impression – Severity of Illness (CGI-S)

The CGI-S is a research rating tool of the subject's current disease state on a 7-point scale of 1 to 7. A value of 0 represents "Not assessed", and the remaining values 1-7 represent "Normal, not at all ill" (1) through to "Among the most extremely ill subjects" (7). Any "Not assessed" items will be treated as missing and not left as zero in analysis datasets.

6.8.3 Drug-Induced Extrapyramidal Symptoms Scale (DIEPSS)

The DIEPSS is a rating tool of extrapyramidal symptoms induced by antipsychotics and consist of 8 individual items and one global assessment; overall severity. The severity of each item is on a 5-point scale of 0 to 4. A value of 0 represents "None, Normal", and the remaining values 1-4 represent "Minimal, Questionable" (1) through to "severe" (4). The items covered include gait, bradykinesia, sialorrhea, muscle rigidity, tremor, akathisia, dystonia, dyskinesia and overall severity. DIEPSS total score is defined as the sum of 8 item scores not including overall severity.

